**4. Subject Recruitment Methods and Privacy: Recruitment:**

[figure not shown]
A total of 400 premature infants born <29 6/7weeks GA will be recruited from the obstetrics admission area and randomized to one of the 4 treatment groups; n=100 each will complete the study (control; DCC alone; Indomethacin alone; DCC + Indomethacin). This facility admits over 800 sick newborn infants/yr and sees a majority of the high-risk obstetrical patients in the Lexington area and beyond. Informed consent will be obtained prior to patient enrollment, by [name] (PI) or another member of the research team experienced at consenting mothers for research studies. There will also be an on-call schedule at night to screen potentially eligible women, enroll them, and attend the births. Women enrolled will be assigned to either immediate or delayed cord clamping groups via a computer generated random number system to assure permuted block randomization. When notified of a subject's impending birth, the research coordinator will open the randomization card, review the protocol with the attending/fellow/or resident obstetrician, and time the cord clamping.

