In summary, a total of 3.7 ml of blood (7 time points during the 0-60 days of life, 0.5mL each, and 2 time points with 0.1ml each), 4 head ultrasound measurements (day of life (DOL) three, first week of life, DOL fourteen and at 30 DOL or later), a head MRI at 38 weeks corrected GA will be obtained from each subject as well as 3 measurements of neurodevelopment (TIMP and Bayley III). Enrolled patients will receive a study number to protect confidentiality of demographic information. Data to be collected is shown on the attached data collection instrument. Only the Co-PIs and study coordinators will know the identities

of the patients and be responsible for the storage of collected data. All data will be de-identified.

Studies shown below are marked as part of standard care or research. The 14 day ultrasound is variable, depending on findings on the 7 day ultrasound. Our standard unit policy is to repeat at 14 days if our routine 7 day ultrasound shows a significant hemorrhage.

Timeline	Procedure	Standard Care	Research
at delivery	umbilical cord blood collection (1-5mL)		X
At admission, 24, 48, & 72hr, Days 7, 30, & 60	blood draw (0.5mL) at each time point	X	
72 hours	head ultrasound		X
7 & 30 days	head ultrasound	X	
7 & 30 days	Serum Cystatin C (0.1mL)		X
14 days	head ultrasound	X	X
Days 30 & 60 if not on vent, or as soon as possible when extubated	neonatal sleep study/pneumogram		X
38 weeks of corrected GA*	head MRI*		X
3-4 months of corrected GA	Test of Infant Motor Performance (TIMP)	X	
6-9 months of corrected GA	Bayley III	X	
18-24 months of corrected GA	Bayley III; Brief infant Toddler Social Emotional Assessment (BITSEA), MCHAT(pass/fail)	X	

\* , Please note that at the initial start of this 5 year study our plan for head MRIs in all enrolled patients is considered a research effort. Note however that the use of head MRI in extremely premature infants that are known to or suspected to have brain lesions is currently common-place and at other institutions is standard care. Therefore it is possible (and perhaps likely) that the routine use of this imaging modality will in coming years become 'standard care' for all preterm infants that are at very high risk of cranial bleeds (e.g. the exact patient group in this study) at our institution. If this becomes the case we will provide amendments to the IRB to account for this issue.

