**Aim 1 Statistical analyses: [all analyses performed as 'intention to treat' where appropriate]:** To investigate the primary hypothesis in Aim 1A (treatment-related outcome differences with respect to the primary endpoint fraction of cases surviving without severe IVH, grade 3 or 4) we will use head ultrasound data from day of life 0-30, and use two distinct approaches. First, based on the qualitative data used to compute the sample size, we will employ a bivariate analysis to identify the significant covariates, followed by a multiple logistic regression analysis to test for differences between the four groups in the presence of significant covariates. Secondly, we will develop severe IVH or PVL data and employ survival analysis statistics (log rank Mantel-Cox test). If the assumptions are validated, we will use the Cox proportional hazard model for this survival data. In addition we will compare head MRI results (measured at the single time point of 38wks adjusted gestational age using a multiple regression model that will incorporate significant covariates. Aim 1B is concerned with comparison of Groups 3 and 4 only (e.g. Indomethacin vs. Indo-DCC) and the procedures developed for the 4 group analysis are also applicable here. For Aim 1C we correlate later performance with the short term brain imaging results in the framework of a multiple regression model where the 4 groups will be used as predictors and will be compared. In all settings we will also perform separate analyses of IVH alone, and PVL alone.

Aim 1 also involves comparisons of nominal/ordinal and continuous variables associated with neurodevelopment and toxicity where single or repeated measures on the response are available. Approaches similar to the one described above will be taken where we first build a statistically valid model that controls for all influential covariates and test the relevant hypotheses in the context of the model. Aim 1B corresponds to the testing of the interaction effect between the ICC/DCC effect and the use of prophylactic indomethacin. Other hypotheses correspond to the main effects. We will also compare the variables that reflect renal function/status (as assessments of potential indomethacin toxicities, other specific comorbidities and hospital stay related variables across the 4 groups.

**Aim 2: Investigate mechanistic effects of prophylactic indomethacin, DCC, and their combination in infants less than 28wks gestational age.**

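### The second Aim 1A analysis fits a Cox model to lesions dated only by a few scheduled scans and states no method for ties or interval-dated events; with Breslow ties it would lose power

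*Combined protocol and SAP*

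**What the plan says.** The SAP (Aim 1 statistical analyses) states the data and the number of approaches: "we will use head ultrasound data from day of life 0-30, and use two distinct approaches". The first approach is logistic regression with covariates. For the second: "we will develop severe IVH or PVL data and employ survival analysis statistics (log rank Mantel-Cox test", and then: "If the assumptions are validated, we will use the Cox proportional hazard model for this survival data". The same procedures are carried over to Aim 1B and to the separate analyses of IVH and of PVL.

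The dates available to this analysis come from section 6 (Research Procedures), which promises for each subject "4 head ultrasound measurements (day of life (DOL) three, first week of life, DOL fourteen and at 30 DOL or later". The same section then says: "The 14 day ultrasound is variable, depending on findings on the 7 day ultrasound". It adds: "Our standard unit policy is to repeat at 14 days if our routine 7 day ultrasound shows a significant hemorrhage".

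The SAP does not define the event time, the handling of ties or interval censoring, the place of death in this analysis, or how a scan after day 30 enters a day 0-30 analysis. It names SAS and SPSS without a tie option.

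**The concern.** The onset of a lesion is never observed. It is known only to lie between the last clear scan and the first abnormal one. Cox regression is built for event times that are nearly all distinct. Here, recorded time is detection time, and most lesion events will share three or four values. How the ties are handled then affects the result noticeably, and the SAP leaves this open. Two analysts following it could report different hazard ratios, intervals and p-values from the same data on one of the two stated routes to the primary hypothesis. The choice could also be made after the results are known.

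**Working it through.** **Inputs from the documents.** Four groups, "n=100 each will complete the study" (section 4); scans near days 3, 7 and 30 for all, with day 14 conditional (section 6). The SAP says the study was powered by chi-square tests for proportions, but gives no event rates, effect size or power. The 100 per group therefore cannot be reproduced, and lesion risk has to be assumed.

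**Assumed.** Two-sided 5% tests; proportional hazards; 75% of the lesion hazard before day 3 (flat onset also tried in the two-arm runs).

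**Step 1: why Breslow shrinks the estimate.** Take the extreme case of all events found at one scan. Under proportional hazards the treated risk is p1 = 1 - (1 - p0)^HR. Breslow then estimates the risk ratio p1/p0. With a true HR of 0.5:

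| Control risk p0 | p1 | Breslow limit p1/p0 | Odds ratio |
|---|---|---|---|
| 15% | 0.078 | 0.520 | 0.480 |
| 30% | 0.163 | 0.544 | 0.456 |
| 50% | 0.293 | 0.586 | 0.414 |

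The last column is what a discrete-logistic treatment of ties would estimate; it errs in the other direction.

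**Step 2: two arms, 100 v 100, scans on days 3, 7 and 30.** 1,000 simulated trials per setting, so the Monte Carlo standard error on a 5% rate is sqrt(0.05 x 0.95/1000) = 0.7 points. Early onset, true HR 0.5:

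| Control risk | Median HR: exact onset / Breslow / Efron | Wald power: exact onset / Breslow / Efron |
|---|---|---|
| 15% | 0.510 / 0.522 / 0.509 | 31.2 / 28.3 / 31.2% |
| 30% | 0.490 / 0.516 / 0.490 | 64.8 / 59.4 / 64.7% |
| 50% | 0.503 / 0.556 / 0.507 | 85.6 / 76.1 / 84.4% |

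Under no effect with early onset, the Breslow model standard error is 0.261 against an empirical 0.235 at 30% risk, and 0.201 against 0.157 at 50%. As a check at 30%: 0.235/0.261 = 0.900, and 1.96/0.900 = 2.18, which implies a two-sided error of 2.9%; the simulation gave 2.6%. Across all settings, early and flat, Breslow Wald error was 0.9-4.0% and Efron 3.5-5.7%. Efron coverage at HR 0.5 was 94.8-96.9%.

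**Step 3: four arms, 100 each, 3-df Wald test, HR 0.65 per factor** (0.65 x 0.65 = 0.42 for the combination). Scans on days 3, 7, 14 and 30, 2,000 runs:

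| Control risk | Type I error: Breslow / Efron | Power: Breslow / Efron |
|---|---|---|
| 15% | 2.6 / 4.1% | 24 / 27% |
| 30% | 1.8 / 4.8% | 51 / 60% |
| 40% | 1.7 / 4.6% | 68 / 80% |

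With scans on days 3, 7 and 30 only, Breslow type I error was 1.7-3.2% and power 4-11 points below Efron over the same risks. When scan days were spread over each window, the loss fell to 1-4 points.

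**Step 4: what is not affected.** On the common schedule, log-rank type I error was 4.2-6.1% with scan dates and 4.2-6.0% with exact onset. Its power with early onset was 65.7% v 65.9% at 30% risk and 85.0% v 85.7% at 50%. The logistic approach uses no lesion dates.

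**Step 5: if scan timing differed by arm.** With no true effect, 30% risk, early onset, and the first two scans one day later in one arm, the median Efron HR was 0.90. Rejection was 6.4% (log-rank) and 7.1% (Efron Wald). With flat onset there was no bias (HR 0.997; 4.2% for both tests). A day-14 scan in one arm only gave a median HR of 0.97-0.99.

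**The case against.** The documents never choose Breslow, so the loss is conditional on an option nobody has selected. The log-rank test comes first and Cox only follows if its assumptions are validated. The error is conservative, and the logistic approach, which matches the proportions-based powering, is untouched. All of this stands. It makes the defect an unstated option rather than a wrong family of methods.

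It can also be argued that deaths have exact dates and would break up the ties if counted as events. This helps little: in a four-arm simulation with 10% exactly dated deaths counted as events, the Breslow loss was still 2-14 points.

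A reader might infer two stronger things. One is that ties invalidate the log-rank test and any Cox fit. The figures above show otherwise on a common schedule with Efron ties. The other is that scan timing differs by arm, because delivery staff know the cord assignment. The documents do not support that. The section 6 timeline is the same for all groups, data are to be recorded by people largely unaware of the assignment, and the delivery neonatologist is expected usually not to give daily care. Differential timing is a possible risk, not a documented one, and its modelled effect in Step 5 is modest.

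**Conclusion.** The concern holds in a limited form: one of the two stated approaches to the primary hypothesis has no method for heavily tied, interval-dated events. If Breslow ties were used, four-arm type I error would be about 2-3% and power about 4-11 points lower than with Efron ties on nominal scan days. The hazard ratio would be pulled modestly towards 1, for example 0.516 for a true 0.5 at 30% risk.

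These sizes rest on assumed control lesion risks of 15-40%, an assumed hazard ratio and onset pattern, and 100 infants per group. The effect is small at 15% risk and grows with risk. The effect of the open-ended last scan was not modelled. The point should be settled before analysis, but it does not undermine the trial.

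**What to change.** Replace the Cox model with a grouped-time proportional hazards model: one record per infant per scan window, complementary log-log link, window as a factor, treatment terms and covariates as planned, and a likelihood ratio test. In each window 1 - p1 = (1 - p0)^HR, so the estimate is still the hazard ratio.

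Use windows that every infant has: to 72 hours, to day 7 and to day 30. Assign any day-14 finding to the day 7-30 window. A separate day-14 record would not work while that scan depends on the day-7 result: coding unscanned infants as lesion-free is unsupported, and dropping them leaves a selected risk set.

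At minimum, fit Cox on those windows with Efron ties, or with exact ties in the form that assumes continuous underlying times; the discrete-logistic form estimates an odds ratio. Run the log-rank test on the same windows rather than on calendar scan dates.

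The SAP should also define the event, state whether death is an event or a competing event, and say how a scan after day 30 is assigned. The two day-14 statements in section 6 must be reconciled.

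The cost is a few sentences in the SAP and a few lines of code, with no new data. The small downside is that scans must be mapped to windows and onset within days 7-30 is not resolved.

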## Study Protocol:

### 1. Objectives:

**Primary GOAL:** Compare efficacy and safety of prophylactic indomethacin, DCC, and their combination, in affecting the incidence and severity of IVH in infants less than 29wks GA at birth.

- **Aim 1A):** Test for differences in primary outcome measure: 'fraction of survivors with no severe IVH or PVL' among the 4 groups, using head ultrasound (1-30d), and head MRI at 38wks adjusted GA.
- **Aim 1B):** Test the hypothesis that DCC improves effectiveness and/or decreases toxicities of indomethacin.
- **Aim 1C):** Test for treatment dependent differences in neurocognitive follow up evaluations and investigate relationships between short term brain imaging results and later neurocognitive performance across treatment groups.

**Secondary GOAL:** Investigate mechanistic effects of prophylactic indomethacin, DCC, and their combination in infants less than 29wks GA.

- **Aim 2A):** Test the hypotheses that blood volume status and/or hemodynamic stability are different between groups (at 0,1,2,3,7, 30, and 60 days of life).
- **Aim 2B):** Test the hypothesis that biomarkers of inflammation and vascular endothelial stress are different between groups (at 0,1,2,3,7, 30, and 60 days of life).
- **Aim 2C):** Test the hypothesis that numbers, or apoptotic frequency, of circulating progenitor cells with endothelial or neuronal phenotype capacity are different between groups (at 0,1,2,3,7, 30 and 60 days of life).
- **Aim 3):** Determine relationships between clinical outcomes (Aim1) and blood measurements (Aim 2) among treatment groups.

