If for any medical reason the bedside/attending Obstetrician or Neonatologist has concerns and wishes to become ‘unblinded’ to the infant’s enrollment, the study participant will be removed from the study. We expect that the only practitioner who is unblinded in the study is the specific Neonatologist at the particular infants’ delivery, who most likely is not performing the daily care for the newborn after admission based on the structure of our delivery room teams and NICU service teams. All study infants will routinely be followed-up at UK NICU Graduate Follow-up Clinic after discharge since these clinicians have the primary responsibilities for this standard clinical service in our institution. Research oversight for neurodevelopmental follow-up will be the responsibility of [name]. The TIMP and Bayley Scales of Infant Development-III (BSID-III) will be administered at 3-4, 6-9, and 18-24 months corrected age; these are the standard follow-up times for collection of such data in our clinic, and the tests proposed has been optimized and defined for these age intervals. All exams will be performed by the same therapist trained in high-risk newborn neurodevelopmental exams to avoid performance biases, and will be blinded to the treatment group. Data will be reviewed quarterly by the research team. Money will be given to families (\$25) for expenses (gas, parking, food) for each of the three follow-up evaluations. Frequent phone contact with project personnel has been another technique successfully used in past research by [name] and colleagues. Project personnel will contact participants every 2 weeks until the first measurement (3-4 months), and then monthly until all measurements are complete for the follow up groups (n=400 completed). Participants will be asked to give multiple phone numbers (work, family, and friends) to make contact more feasible; participants who move or change phone numbers will receive gift certificates (\$25) if they contact research personnel with their new address or phone number. Some attrition (~5%) is anticipated and is built into the sample size calculation.

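### Aim 1C gives infants who die before follow-up no place in the comparison of neurocognitive scores, so as written it compares assessed survivors and is not protected by randomisation

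*Combined protocol and SAP*

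**What the plan says.** Section 1 (Objectives) makes Aim 1C in part a treatment comparison: "Test for treatment dependent differences in neurocognitive follow up evaluations". Its other part relates early brain imaging to later performance. Under section 6 (Research Procedures) the TIMP and Bayley III "will be administered at 3-4, 6-9, and 18-24 months corrected age".

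The Statistical analysis plan, under the Aim 1 analyses, places Aim 1C "in the framework of a multiple regression model where the 4 groups will be used as predictors and will be compared". It adds that Aim 1 involves "comparisons of nominal/ordinal and continuous variables associated with neurodevelopment and toxicity where single or repeated measures on the response are available", to be handled by covariate-adjusted models. The heading of that section reads "all analyses performed as 'intention to treat' where appropriate". It does not say what this means for an infant with no score.

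Survival appears in the primary endpoint. The Aim 1 analysis text describes "treatment-related outcome differences with respect to the primary endpoint fraction of cases surviving without severe IVH, grade 3 or 4". The Objectives word it as "fraction of survivors with no severe IVH or PVL".

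Section 6 describes contact with families every two weeks and "then monthly until all measurements are complete for the follow up groups (n=400 completed". Enrolment is also 400 (section 3). Section 6 allows for about 5% attrition and does not mention death.

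**The concern.** A neurocognitive score cannot exist for an infant who has died. The plan has no composite of death and impairment, no ranking of death, no stated survivor population and no sensitivity analysis for Aim 1C. A regression on scores then drops the deaths without anyone having decided that it should.

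The infants who remain were selected by an event after randomisation. If one treatment keeps alive some very sick infants who would otherwise have died, its assessed group contains more infants at high risk of impairment and can look worse without having harmed anyone. A treatment with more deaths can look better for the same reason. Adjustment for baseline covariates need not repair this. At stake is the long-term treatment comparison of Aim 1C, not the primary ultrasound endpoint.

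**Working it through.** **What can be reproduced.** The documents give no mortality rate, no Bayley mean or standard deviation, and no rates or power for the sample size, so there is no stated figure for this point to reproduce. One side check is possible. If 400 are enrolled and 5% are lost, 400 × 0.95 = 380 are assessed, before any deaths. The 400 follow-up completers therefore leave no visible room for deaths. That is a separate sample-size matter and does not show how deaths would be analysed.

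**Assumptions, none from the documents.**
- Mortality before assessment is *mc* in control and *mt* in a treated arm, with *mt* no higher than *mc*.
- Every infant who would survive under control would also survive under treatment. The treated arm adds extra survivors.
- Treatment changes no infant's score.
- Extra survivors score *g* points below the others, with *g* = 10 to 15.
- For the error rate: 100 infants per arm, 5% attrition among survivors, SD 15, normal approximation, two-sided 0.05.

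**Spurious difference in mean score.** Extra survivors make up (*mc* − *mt*)/(1 − *mt*) of the treated survivors, so the bias is −[(*mc* − *mt*)/(1 − *mt*)] × *g*.

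| Mortality, control v treated | Extra survivors as share of treated survivors | Bias, *g* = 10 to 15 | Type I error |
|---|---|---|---|
| 20% v 20%, same infants surviving | 0 | 0 | 5.0% |
| 20% v 15% | 0.05/0.85 = 0.059 | −0.6 to −0.9 | 5.7% to 6.6% |
| 20% v 10% | 0.10/0.90 = 0.111 | −1.1 to −1.7 | 7.6% to 10.9% |

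For scale, at 20% v 10% the numbers assessed are 100 × 0.80 × 0.95 = 76 and 100 × 0.90 × 0.95 = 85.5. The standard error of the difference is 15 × √(1/76 + 1/85.5) = 2.4 points.

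**Direction.** Take 20% v 10% mortality, with impairment assumed at 20% in infants who would survive either way and 40% in the extra survivors.
- Impairment among survivors: control 20.0%; treated (0.80 × 0.20 + 0.10 × 0.40)/0.90 = 22.2%. The treated arm looks worse.
- Death or impairment among all randomised: control 0.20 + 0.80 × 0.20 = 36%; treated 0.10 + 0.90 × 0.222 = 30%. The treated arm is better.

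The same infants give opposite answers according to whether deaths are counted.

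**The case against.** **The plan does not state a survivor restriction.** A reader might infer one from the phrase about measures being available. The phrase covers toxicity as well as neurodevelopment, and it can be read simply as distinguishing one measurement per infant from several. This stands. The restriction follows from the plan's silence on deaths together with a regression on scores, not from an explicit rule.

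**The trial does not say it expects to change survival.** A reader might infer this because survival is in the primary endpoint. The documents hypothesise no mortality effect and quantify none. The stated goal concerns the incidence and severity of IVH, an endpoint can include survival only because death prevents imaging, and the Objectives wording can be read as conditional on survival. This also stands. What remains is that the Aim 1 analysis text counts survival as part of the outcome, so a difference between arms cannot be ruled out in advance.

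**The bias may be nil or small.** With equal mortality and no effect on who survives it is zero, and in the illustrated cases it is below one standard error. That limits the size of the concern. It does not supply the missing rule, and a rule chosen after deaths by arm are known would carry little weight.

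**Intention to treat is already stated.** It is qualified by appropriateness and says nothing about infants without a score, so it does not settle the matter.

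**A composite changes the question.** It does, and part of Aim 1C cannot use one: the relation of imaging to later performance can only be studied in assessed infants. Both points are accepted in the fix.

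**Conclusion.** The concern holds as a gap in the plan. Aim 1C compares treatments on scores that infants who die cannot have, and gives those infants no place in the comparison. As written, it is a comparison of assessed survivors without the protection of randomisation.

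Whether this produces bias depends on whether treatment affects who survives, which the documents neither assert nor exclude. On the stated assumptions the spurious difference runs from 0, through about 0.6-0.9 points (20% v 15% mortality), to about 1.1-1.7 points (20% v 10%). The direction of an impairment comparison can reverse. All mortality, score and impairment values are illustrative.

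The plan should be changed, but the point bears on a follow-up objective and leaves the primary endpoint untouched.

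**What to change.** For the treatment comparison in Aim 1C at 18-24 months, prespecify one of the following among all randomised infants:
- death or Bayley III below a stated cut-off, analysed with the logistic model of Aim 1A; or
- a comparison by ranks, with death ranked below every observed score.

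With either choice:
- State how living infants lost to follow-up are handled, for example by multiple imputation, and keep them distinct from deaths.
- Record vital status at the family contacts already planned in section 6.
- Report deaths and each component by arm.
- Keep the score regressions in survivors as supportive.
- Leave the imaging-versus-performance analysis in assessed survivors, and label it so.

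The cost is mainly SAP wording. The data collection instrument is not among the documents and the schedule in section 6 does not list vital status, so recording late deaths may be a small addition. The downside is that the composite mixes death with impairment, so its components must always be shown separately.
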